6.2 Exclusion criteria

Exclusion criteria for part 1 (CHICO)

- 1. Subjects aged 0 to 27 days who, at birth, were pre-term (i.e., gestational age less than 37 weeks), weighed less than 2500 g, or had a maximum Apgar score <7 at 5 minutes
- 2. Subjects with any of the following conditions that is associated with Chagas' disease, such as:
 - Known evidence of Chagas' disease-related cardiomyopathy/Chagas' heart disease
 - Known evidence of Chagas' disease-related gastrointestinal dysfunction (e.g., megaesophagus, megacolon, or both) or Chagas' digestive disease
 - Serious manifestations of acute Chagas' disease, including myocarditis, meningoencephalitis, or pneumonitis
 - Known evidence of Chagas' disease-related damage to the peripheral nervous system or peripheral neuropathy (i.e., affected subjects show a combination of sensory impairment and diminished tendon reflexes that mainly involve the lower limbs)
 - Clinically significant psychiatric disorder (e.g., moderate to severe depression, severe anxiety, or psychosis) or epilepsy
- 3. Subjects with contraindications/warnings to nifurtimox administration, or with conditions that may increase the risk of the undesirable effects of nifurtimox, including:
 - Hypersensitivity to nifurtimox or any hydantoin, or to any of the excipients
 - Suspected or known porphyria
 - Severe renal impairment defined by the following:
 - For subjects < 1 year of age at randomization, estimated glomerular filtration rate (eGFR) < 100% of the lower limit of normal (LLN) appropriate for age (eGFR should be calculated according to Schwartz formula; see Section 16.2)⁹²

⁹² Text revised for clarity; cross-reference renumbered to 16.2 (Amendment 1)

	Integrated Clinical Study Protocol BAY A2502 / 16027	
03 NOV 2020	Version 11.0	Page: 38 of 259

- For subjects \ge 1 year to < 18 years of age at randomization, eGFR < 80% of LLN appropriate for age
- Severe hepatic impairment (alanine aminotransferase [ALT] or aspartate aminotransferase [AST] considered clinically significant by the investigator)
- History of brain injury, predisposition to seizures or epilepsy, psychiatric disease, or serious behavioral alteration
- Severe or significant gastrointestinal disorders, or metabolism and nutrition disorders
- 4. Subjects with a history of malignancy in the previous 5 years
- 5. Subjects who are chronic abusers or current users of alcohol or recreational drugs, or the newborn infants of mothers who are chronic abusers or current users of alcohol or recreational drugs
- 6. Subjects with any condition that would prevent him/her from taking oral medication
- 7. Immuno-compromised subjects (e.g., those with human immunodeficiency virus infection, primary immunodeficiency, or prolonged treatment with corticosteroids or other immunosuppressive drugs)
- 8. Subjects with any other acute or chronic health conditions or congenital disorders which, in the opinion of the investigator, would make them unsuitable for participation in a clinical study or may interfere with the efficacy, safety, and/or PK evaluation of the study drug
- 9. Subjects who have had previous treatment with trypanocidal agents or an accepted indication for antiparasitic therapy (e.g., reactivation of Chagas' infection due to immunosuppression by several diseases or treatment with steroids)
- Subjects who have had treatment with any investigational medicinal product within 30 days before the first dose of study drug or⁹³ have previously received the study treatment
- 11. Subjects who are pregnant or breastfeeding
- 12. Subjects of breastfeeding mothers under treatment with trypanocidal agents
- 13. Subjects who the investigator considers unlikely to adhere to the protocol, comply with study drug administration, or complete the clinical study and follow-up
- 14. Subjects with close affiliation with the investigational site; e.g., a close relative of the investigator, dependent person (e.g., employee or student of the investigational site)
- 15. Subjects living in housing conditions where there is no active or effective vector-control to *T. cruzi* reinfection as determined by Ministry of Health guidelines in each country

Exclusion criteria for part 2 (CHICO SECURE)

1. Subjects with acute or chronic health conditions or congenital disorders which, in the opinion of the investigator, would make them unsuitable for participation in the clinical study

⁹³ Clarified as per amendment 2

	Integrated Clinical Study Protocol	
	BAY A2502 / 16027	
03 NOV 2020	Version 11.0	Page: 39 of 259

- 2. Subjects living in housing conditions where there is no active or effective vector-control to *T. cruzi* reinfection as determined by Ministry of Health guideline of the respective country and the judgement of the investigator
- 3. Subjects with clinical manifestations of Chagas' disease, such as:
 - Known evidence of Chagas' disease-related gastrointestinal dysfunction (e.g., megaesophagus, megacolon, or both) or Chagas' digestive disease
 - Serious manifestations of acute Chagas' disease, including myocarditis, meningoencephalitis, or pneumonitis
- 4. Immuno-compromised subjects (e.g., those with human immunodeficiency virus infection, primary immunodeficiency, or prolonged treatment with corticosteroids or other immunosuppressive drugs)
- 5. Subjects who the investigator considers unlikely to adhere to the protocol, or complete the long-term follow-up
- 6. Subjects with close affiliation with the investigational site; e.g., a close relative of the investigator, dependent person (e.g., employee or student of the investigational site)

Justification of selection criteria for part 2 (CHICO SECURE)

This LTFU has been designed at the request of the US FDA to assess the incidence of seronegative conversion in subjects who were randomized and received at least one dose of nifurtimox treatment for 4 years after end of nifurtimox treatment.

For assessment of conversion of serological response to negative, 2 distinct serologic tests are recommended that use different techniques and/or detect antibodies to different antigens. Two commonly used techniques are ELISA and IHA.

The exclusion criteria are valid for known or suspected conditions and are chosen to ensure that subjects with conditions which may have an effect on the aims of the follow-up are excluded.

Considering that the follow-up period is evaluating long-term seronegative conversion and OD reduction measured by ELISA after nifurtimox treatment, subjects who required antitrypanosomal treatment, including any investigational treatment for Chagas' disease after nifurtimox regimens will be analyzed separately.

To reduce the risk of reinfection as a confounding factor in the study, subjects residing in areas where vector control has not been instituted are excluded as well.

6.3 Withdrawal of subjects from study

In general, the criteria, rules, and procedures in this section apply to part 1 and part 2 of the study. Criteria, rules, and procedures not applicable to either part of the study are otherwise marked.

6.3.1 Withdrawal

Withdrawal criteria

Subjects *must* be withdrawn from the study if any of the following occurs:

• At their own request or at the request of their parents' or legally acceptable representative. At any time during the study and without giving reasons, a subject may

	Integrated Clinical Study Protocol	
	BAY A2502 / 16027	
03 NOV 2020	Version 11.0	Page: 40 of 259

decline to participate further. The subject will not suffer any disadvantage as a result of this decision.

- Pregnancy. If any urine pregnancy test is positive, a serum pregnancy test must be performed to confirm the result. See Section 9.6.2.⁹⁴ (not applicable to part 2)
- Subjects, with positive parasitology test at the 30-day visit for whom (1) it has been determined that the drug was administered correctly and (2) the daily dosage given was correct, must be discontinued from the study and treated with an alternative trypanocidal medication, selected by the investigator.⁹⁵ (not applicable to part 2)

Subjects *may* be withdrawn from the study if any of the following occurs:

- If, in the investigator's opinion, continuation of the study would be harmful to the subject's well-being
- At the specific request of the sponsor and in liaison with the investigator (e.g., obvious non-compliance, safety concerns)
- For the following situations that are regarded by the investigator to be related to the use of study drug (nifurtimox) (not applicable to part 2):
 - Severe nervous system disorders such as seizure, vertigo/dizziness, polyneuropathy, or peripheral neuropathy
 - Severe gastrointestinal disorders, severe decreased appetite
 - Significant loss of body weight in the judgment of the investigator
 - Severe hepatic impairment
 - Severe renal impairment
 - Psychic disorders such as disorientation, psychotic behavior
 - Development of malignant disease
 - Hematological abnormalities such as severe leukopenia

Depending on the time point of withdrawal, a withdrawn subject is referred to as either "screening failure" or "dropout" as specified below:

Screening failure

A subject who, for any reason (e.g., failure to satisfy the selection criteria), terminates the study before the time point used for the definition of "dropout" (see below) is regarded as a "screening failure."

Re-starting the defined set of screening procedures to enable the "screening failure" subject's participation at a later time point is allowed only in the following situations (not applicable to part 2):

⁹⁴ Third bullet point and text re: positive microscopy deleted (Amendment 1)

⁹⁵ Text added as per amendment 2

	Integrated Clinical Study Protocol BAY A2502 / 16027	
03 NOV 2020	Version 11.0	Page: 41 of 259

- The subject had successfully passed the screening procedures, but could not start subsequent treatment on schedule.
- Initial screening occurred too early to complete the required washout period (Day -14 to Day -1) after prior therapy.
- The in-/exclusion criteria preventing the subject's initial attempt to participate have been changed (via protocol amendment).

Subjects not meeting inclusion/exclusion criteria at screening may be re-screened once. At the discretion of the investigator and in consultation with Bayer, the screening period (or rescreening period) may be extended up to 3 days to allow for receipt of test results, to evaluate changes in a subject's condition, or for reasons not under the subject's control.⁹⁶ In any case, the investigator has to ensure that the repeated screening procedures do not expose the subject to an unjustifiable health risk. Also, for re-screening, the subject has to re-sign the informed consent form, even if it was not changed after the subject's previous screening. Only the re-screening will be captured in the eCRF.⁹⁷ (Not applicable to part 2)

Dropout

A subject who discontinues study participation prematurely for any reason is defined as a "dropout" if the subject has already been randomized, assigned to treatment, and administered at least one dose of study drug.

General procedures

In all cases, the reason for withdrawal must be recorded in the electronic case report form (eCRF) and in the subject's medical records.

The subject may object to the generation and processing of post-withdrawal data as specified in Section 13.4.

Any subject removed from the study will remain under medical supervision until discharge or transfer is medically acceptable.

Details for the premature termination of the study as a whole (or components thereof) are provided in Section 12.

6.3.2 Replacement

A subject who is withdrawn from the study will not be replaced.

6.4 Subject identification

After documentation of consent/assent (informed consent/assent form) by the parent(s) and assent by the child in accordance with local regulations (varies in each country), each subject will be assigned a 9-digit number for unambiguous identification throughout the study constructed as follows:

⁹⁶ Text modified as per amendment 4

⁹⁷ Text regarding screening failure and re-screening modified/added for clarity (Amendment 1)

Integrated Clinical Study Protocol BAY A2502 / 16027		
03 NOV 2020	Version 11.0	Page: 42 of 259
Digits 1 to 2	= Country code	
Digits 3 to 5	5 = Center number within the country	
(Digits 1 to 5	= Trial unit)	
Digits 6 to 9	= Current subject number within the center	

1 CI: 1 CI 1 D

Subject identification numbers must be used in sequence, and no number should be skipped, substituted, or reused.

7. Treatment(s)

7.1 Treatments to be administered

Each subject will receive nifurtimox oral tablets three times daily for 60 days, or for 30 days followed by nifurtimox placebo administered three times daily for 30 days.⁹⁸

Each nifurtimox tablet contains either 30 mg or 120 mg of nifurtimox as the active ingredient, and the following excipients: calcium hydrogen phosphate dehydrate, maize starch, silica colloidal anhydrous, and sodium lauryl sulfate.

7.2 Identity of study treatment

Nifurtimox 30-mg and 120-mg oral tablets and matching placebo tablets for each dosage form will be provided by Bayer HealthCare AG. The tablets for both dosage forms are yellow, round, and biconvex. The matching placebo tablets for each dosage (30-mg and 120-mg formulations) will bear the same appearance and packaging as the active study drug tablets.⁹⁹

All study drugs will be labeled according to the requirements of local law and legislation. Label text will be approved according to the sponsor's agreed procedures, and a copy of the labels will be made available to the study site upon request.

For all study drugs, a system of numbering in accordance with all requirements of Good Manufacturing Practice (GMP) will be used, ensuring that each dose of study drug can be traced back to the respective bulk batch of the ingredients. Lists linking all numbering levels will be maintained by the sponsor's clinical supplies Quality Assurance group.

A complete record of batch numbers and expiry dates of all study treatment as well as the labels will be maintained in the sponsor's study file.

7.3 Treatment assignment

Subjects will be randomized via IVRS/IWRS to one of two treatment groups in a 2:1 ratio (60-day regimen vs. 30-day regimen) as follows:

- Nifurtimox tablets administered three times daily for 60 days (Days 1 60, active nifurtimox treatment, Treatment Group 1), or
- Nifurtimox tablets administered three times daily for 30 days, followed by nifurtimox placebo administered three times daily for 30 days (Days 1 30, active nifurtimox treatment; Days 31 60, placebo; Treatment Group 2).

⁹⁸ Last sentence deleted since it appears later in Section 7.4 (Amendment 1)

⁹⁹ Text modified for clarity (Amendment 1)

	Integrated Clinical Study Protocol BAY A2502 / 16027	
03 NOV 2020	Version 11.0	Page: 43 of 259

7.4 Dosage and administration

Nifurtimox oral tablets will be administered in recommended doses by body weight according to the company core data sheet (CCDS; Table 7–1). For infants and children weighing more than 6.0 kg and < 40kg, the daily dosage will be 10-20 mg/kg. Total daily dosages for adolescents weighing > 40 mg will be 8-10 mg/kg, slightly lower than that recommended in the CCDS, to minimize the likelihood of adverse experiences.

Table 7–1: Total daily dosage of nifurtimox oral tablets based on body weight

Body weight group	Total daily dose of nifurtimox [mg / kg body weight]
Adolescents (40 – 60 kg)	8-10
Infants and children (<40 kg)	10-20

Study drug will be dispensed at Visits 2 (Day 1) and 6 (Day 30), with instructions for administration.¹⁰⁰ Dosages of study drug dispensed at Visits 2 and 6 will be the same even if a different dosage is indicated based on a patient's weight change.¹⁰¹ Nifurtimox will be administered three times a day, in the morning, at noon, and at night, with food. The 30-mg and 120-mg tablets have score lines and can be divided into two equal halves to allow for 15-mg or 60 mg dose increments, respectively. The tablet is manufactured for quick disintegration in order to allow administration to subjects < 6 years old who are not able to swallow tablets. Before administration, the tablet should be dissolved in enough water to fill a teaspoon (approximately 5 mL) to form a soft slurry¹⁰² that should be given immediately with food. Nifurtimox will be dispensed based on body weight at randomization, as presented in Table 7–2.¹⁰³

Age Group	Body Weight (kg) ¹⁰⁵	Number of 30-mg Tablets	Number of 120-mg Tablets
	2.5 – 4.5	3 x daily 1/2 tablet	
	4.6 - <9	3 x daily 1 tablet	
	9 - <13	3 x daily 1 1/2 tablets	
	13 - <18	3 x daily 2 tablets	
	18 - <22	3 x daily 2 1/2 tablets	
	22 - <27	3 x daily 3 tablets	
	27 - <35	3 x daily 3 1/2 tablets	
	35 - <41		3 x daily 1 ¹ / ₂ tablets
\geq 12 to < 18 years	41 - <51		3 x daily 1 tablet
-	51 - < 71		3 x daily 1 ¹ / ₂ tablets
	71 - < 91		3 x daily 2 tablets
	91 or greater		3 x daily 2 1/2 tablets

Table 7–2: Individual dosages of nifurtimox oral tablets based on body weight¹⁰⁴

103 Text modified for clarity (Amendment 1)

¹⁰⁰ First sentence added for clarity (Amendment 1)

¹⁰¹ Text modified as per amendment 4

¹⁰² Bioequivalence testing of the slurry has determined it to be comparable to 4 x 30-mg tablets and the 120-mg tablet.

¹⁰⁴ Table 7-1, Table 7-2 and associated text in dosage and administration modified as of amendment 2

¹⁰⁵ In this column, upper limit of weight ranges in each category changed per the most current dosing information (Amendment 1)

	Integrated Clinical Study Protocol	
	BAY A2502 / 16027	
03 NOV 2020	Version 11.0	Page: 44 of 259

At Visits 2 and 6, when study drug is dispensed, subjects/legally authorized representatives will be provided with a diary on which to document the date, exact time, and doses (morning, noon, and night) of study drug, and comments (see Section 1). Should a subject vomit or spit out study drug, the occurrence will be recorded on the diary along with the time of the event.¹⁰⁶ Subjects/legally authorized representatives will be instructed to bring their diaries with them to each in-clinic study visit. The diaries will be collected and reviewed at each study visit to perform drug accountability and assess treatment compliance.¹⁰⁷

Riboflavin is included as a colorant in the matching placebo tablets for study drug blinding purposes. A common side effect of riboflavin ingestion is bright yellow urine. Subjects and/or their legally authorized representatives will be advised of the possibility of change in the subject's urine color within the informed consent form, and when study drug is administered and dispensed at the investigational site.¹⁰⁸

Subjects consenting to optional PK assessments must withhold taking the morning dose of study drug on the day of Visits 3, 6, and 8, when pre- and post-dose PK blood samples will be obtained. Subjects not consenting to optional PK assessments may take their study drug on the mornings of Visits 3, 6, and 8 as instructed.¹⁰⁹

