	• Assess the occurrence of congenital infect	ion with T. cruzi in children

⁶ Text modified per Modification 2 (Amendment 1)
⁷ Text modified per Modification 2 (Amendment 1)
⁸ Text modified per Modification 2 (Amendment 1)

⁹ Fourth objective added per Modification 2 (Amendment 1)

	BAY A2502 / 16027
03 NOV 2020	Version 11.0 Page: 6 of 25
	born of female subjects who were randomized and received at least one dose of the 60- or 30-day nifurtimox treatment regimen. The congenital infection will be confirmed by parasitological method in children ≤8 months of age and by serological method in children >8 months of age.
Test drug(s)	Nifurtimox 30-mg and 120-mg tablets with score lines to be divided into two equal halves to allow for 15-mg and 60-mg dose increments, respectively.
Name of active ingredient	Nifurtimox
Dose(s)	For pediatric subjects with body weight ≤ 40 kg: 10-20 mg/kg/day in three divided doses
	For pediatric subjects with body weight > 40 kg: $8 - 10$ mg/kg/day in three divided doses. The planned mg/kg per day dosages are as in the Company Core Data Sheet.
Route of administration	Oral tablets, to be administered with food
Duration of treatment	60 days of nifurtimox (Treatment Group 1), or 30 days of nifurtimox followed by 30 days of placebo (Treatment Group 2)
Reference drug(s)	None
Indication	Treatment of Chagas' disease in children younger than 18 years of age
Diagnosis and main criteria for inclusion /exclusion	 Part 1 (CHICO) Male and female pediatric subjects aged 0 days to younger than 18 years Chagas' disease diagnosed/confirmed by: Subjects < 8 months of age at randomization must demonstrate direct observation of Trypanosoma cruzi by concentration test Subjects ≥ 8 months to < 18 years of age at randomization must demonstrate a positive conventional ELISA result for both of the following tests to confirm diagnosis: Recombinant ELISA Total purified antigen ELISA Additionally, a non-conventional ELISA test and indirect hemagglutination assay (IHA) will be obtained; however, a positive result will not be required for diagnosis. 10,11 Subjects will also be eligible if there is acceptable documentation of positive Chagas' disease within three months prior to screening and they have not had prior anti-trypanocidal or anti-parasitic treatment. 12 Written informed consent by the subject and/or parent(s) or legally authorized representative(s) according to the age established per local regulations must be

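### Table 7-2 dispenses daily doses outside the protocol's stated mg/kg ranges at several body weights, and the 40 kg cut-point and core-data-sheet statements conflict

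*Protocol*

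**What the plan says.** Dosing by weight is described in four places in the Protocol.

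- **Synopsis, Dose(s).** Up to and including 40 kg: "10-20 mg/kg/day in three divided doses". The next entry begins "For pediatric subjects with body weight > 40 kg" and gives 8-10 mg/kg/day. It adds: "The planned mg/kg per day dosages are as in the Company Core Data Sheet".
- **Section 7.4, text.** "For infants and children weighing more than 6.0 kg and < 40kg, the daily dosage will be 10-20 mg/kg". For heavier subjects: "Total daily dosages for adolescents weighing > 40 mg will be 8-10 mg/kg, slightly lower than that recommended in the CCDS". The same paragraph opens by saying that dosing follows the core data sheet.
- **Table 7-1.** Two rows: "Infants and children (<40 kg") at 10-20 mg/kg, and "Adolescents (40 – 60 kg") at 8-10 mg/kg. There is no row above 60 kg.
- **Table 7-2.** Tablet counts for twelve weight bands, from 2.5 kg to 91 kg and above. The count falls between the 35 to <41 kg and 41 to <51 kg bands.

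Table 7-2 is the operative one: "Nifurtimox will be dispensed based on body weight at randomization, as presented in Table 7–2". Section 7.4 also keeps the dose unchanged at Visit 6 even if weight has changed.

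**The concern.** Tablet counts and mg/kg ranges describe the same dose, so each should reproduce the other. Where they do not, a site that follows Table 7-2 exactly gives a dose that the same section says will not be given.

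Three things rest on this:

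- Sites dispense by the table.
- Protocol 6.3.1 requires withdrawal, and a switch to another drug, for a subject with positive parasitology at the 30-day visit, provided the drug was properly taken and the dose was the right one. At the mismatched weights that second condition has two answers, depending on which part of the protocol is consulted.
- The planned analyses would not show the mismatch. SAP 6.1.4 measures compliance as tablets taken over tablets planned, and the per-protocol rule in SAP 5.1 uses assigned doses. A subject whose assigned dose lies outside the stated range can score 100% on both. SAP 6.1.4 summarises exposure by dose but does not mention mg/kg.

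**Working it through.** **Inputs.** Tablets per intake, strength (30 or 120 mg) and weight bands come from Table 7-2, with three intakes a day. Stated ranges come from the synopsis, the 7.4 text and Table 7-1.

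**Formula.** Daily dose D = 3 × tablets per intake × strength. mg/kg/day = D / weight, taken at both ends of each band. The weight at which a band crosses a limit L is D / L.

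| Weight (kg) | Per intake | D (mg/day) | mg/kg at lower end | mg/kg at upper end | Stated |
|---|---|---|---|---|---|
| 2.5-4.5 | ½ × 30 | 45 | 18.0 | 10.0 | 10-20 |
| 4.6-<9 | 1 × 30 | 90 | 19.6 | 10.0 | 10-20 |
| 9-<13 | 1½ × 30 | 135 | 15.0 | 10.4 | 10-20 |
| 13-<18 | 2 × 30 | 180 | 13.8 | 10.0 | 10-20 |
| 18-<22 | 2½ × 30 | 225 | 12.5 | 10.2 | 10-20 |
| 22-<27 | 3 × 30 | 270 | 12.3 | 10.0 | 10-20 |
| 27-<35 | 3½ × 30 | 315 | 11.7 | 9.0 | 10-20 |
| 35-<41 | 1½ × 120 | 540 | 15.4 | 13.2 | 10-20, then 8-10 above 40 kg |
| 41-<51 | 1 × 120 | 360 | 8.8 | 7.1 | 8-10 |
| 51-<71 | 1½ × 120 | 540 | 10.6 | 7.6 | 8-10 |
| 71-<91 | 2 × 120 | 720 | 10.1 | 7.9 | 8-10 |
| 91 and above | 2½ × 120 | 900 | 9.9 | no upper end | 8-10 |

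**Where it agrees.** All six bands below 27 kg reproduce the stated 10-20 mg/kg.

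**Where it does not.**
- 27-<35 kg: 315 / 10 = 31.5 kg. Above that the dose is under 10, falling to 315 / 35 = 9.0.
- 35-<41 kg: inside 10-20 up to 40 kg. Just above 40 kg it is 540 / 40 = 13.5, and towards 41 kg it is 540 / 41 = 13.2, against 8-10.
- 41-<51 kg: 360 / 8 = 45 kg. Above that the dose is under 8, falling to 360 / 51 = 7.1.
- 51-<71 kg: 540 / 10 = 54 kg, so 51 to <54 kg gets more than 10 (up to 10.6). 540 / 8 = 67.5 kg, so above that the dose is under 8 (down to 7.6).

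**The cut-point.** Exactly 40 kg is 10-20 mg/kg in the synopsis and 8-10 in Table 7-1. The 7.4 text assigns it to neither group, since it uses strict inequalities on both sides and prints mg for kg in one of them. Table 7-2 changes at 41 kg and gives 13.5 mg/kg at 40 kg. Table 7-1 stops at 60 kg, although Table 7-2 continues past 91 kg.

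**The core data sheet.** The synopsis says the planned doses match it. Section 7.4 says adolescent doses are lower than it. Both cannot hold.

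**The case against.** The arithmetic is not in dispute; its weight is. These objections have force:

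- **The drop from 540 to 360 mg/day at 41 kg** might be read as an error in itself. It is not. At 40 kg the two stated ranges are 400-800 mg (10-20 × 40) and 320-400 mg (8-10 × 40), so a lower total for the heavier group is built into the stated rule. Only the position of the switch conflicts.
- **The 71-<91 kg band** misses by about 0.1 mg/kg at each edge. That is rounding.
- **Subjects of 6.0 kg or less, or above 60 kg,** might seem to have no stated range. They do. Table 7-1 and the synopsis set no lower bound, and the synopsis and 7.4 text cover everything above 40 kg.
- **Tablet size limits the fit.** With 120-mg tablets alone, in half-tablet steps three times a day, doses move by 180 mg/day. The 360 mg dose fits 8-10 only up to 45 kg and the 540 mg dose only from 54 kg. The ranges may have been meant as approximate, but nothing in the Protocol says so.
- **The above-40 to <41 kg mismatch** covers 1 kg and is clearest under the synopsis. Section 7.4 and Table 7-1 attach 8-10 to adolescents, and the age column of Table 7-2 is blank for the lighter rows in the available text.
- **The withdrawal rule may seldom reach these weights.** Table 9-1 schedules the concentration test only for subjects under 8 months, who are far lighter than 31.5 kg. The rule reaches the affected weights only if qPCR counts as a parasitology test, which 6.3.1 does not settle.

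A reader might also infer that efficacy and safety would be reported for a regimen nobody received. The documents do not support that: the regimens compared are 60 and 30 days, and both arms use the same Table 7-2.

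The mismatches at 31.5-<35, above 40 to <41, 45-<51, 51-<54 and above 67.5 to <71 kg remain, as do the cut-point and core-data-sheet conflicts.

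**Conclusion.** The Protocol contradicts its own dose figures. The largest departures from the nearest stated limit are 13.5 against 10 just above 40 kg (35% over), 7.1 against 8 towards 51 kg (360 / 51 = 7.06, about 12% under) and 9.0 against 10 towards 35 kg (10% under). In 51-<71 kg they are about 6% over and 5% under.

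This rests on three readings. The printed mg in 7.4 is taken as kg. Table 7-2 is taken as extracted; versions in the amendment log carry the same 35-<41 kg entry, which makes a reading error there unlikely. Above 60 kg the comparison uses the synopsis and 7.4 text, because Table 7-1 has no row.

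The documents give no weight distribution, so the number of subjects affected is unknown; it depends on how many weigh more than 31.5 kg. No hypothesis test, estimate or power calculation changes. Nothing here shows which figure is right, or that any subject was over- or under-treated.

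**What to change.** 1. **Protocol.** Reconcile the synopsis, the 7.4 text, Table 7-1 and Table 7-2 on three things: the mg/kg range that applies to each weight band, the cut-points (including exactly 40 kg and the upper end of Table 7-1), and the relation to the core data sheet. Correct the unit in 7.4. If the ranges are meant as approximate, say so. The sponsor's clinical team decides which passage is right. State also which of them defines the right dose for the withdrawal rule in 6.3.1.
2. **SAP 6.1.4.** Add a descriptive summary of actual mg/kg/day by Table 7-2 weight band and regimen, from tablets taken and weight at randomisation.

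The cost is a protocol clarification and one exposure table from data already collected. Section 7.8 provides for no study drug in Part 2. If Part 1 dosing is finished, the table still lets the 12-month and 4-year results be read against the dose actually taken.
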